⁵ Vital signs to include BP, HR, respiration rate, and oral/tympanic temperature; triplicate BP and HR measurements (separated by approximately 1 minute) after subject is supine for 5 minutes; vital signs will be obtained at every study visit as follows:

- Screening
- Day 1 of each treatment period:
 1. Prior to dosing (within 15 minutes)
 2. 1 hour (\pm 30 mins) after dosing
- Day 7 of each treatment period: 1 hour (\pm 30 mins) after dosing
- Day 14 of each treatment period: 1 hour (\pm 30 mins) after dosing
- Follow-Up Visit

⁶ Subjects will be required to rest in a supine position for at least 5 minutes prior to the recording of ECG. ECGs to be obtained at the following timepoints:

- Screening
- Lead-In
- Day 1 of each treatment period:
 1. Prior to dosing (within 15 minutes)
 2. 1 hour (\pm 30 mins) after dosing
 3. 4 hours (\pm 30 mins) after dosing
- Day 14 of each treatment period:
 1. 1 hour (\pm 30 mins) after dosing
 2. 4 hours (\pm 30 mins) after dosing
- Follow-Up Visit

⁷ A complete physical examination (PE) (excluding genital, rectal and breast exams) is required at Screening; the Follow-Up PE will be symptom-driven based on subject complaints.

⁸ Safety labs to include hematology, chemistries, and urinalysis. Subjects should be fasting for 8 hours for the safety labs.

⁹ At Screening, serum β -hCG pregnancy test for females of childbearing potential; an FSH test will be performed for postmenopausal women. Females of childbearing potential will have serum or urine pregnancy tests (per standard site practice) on Day 1, Day 14 and at the Follow-Up visit.

¹⁰ Subjects to be assessed for current infection per local site standard procedure.

¹¹ PK sample timepoints (CST-103/CST-107) in each treatment period:

- Day 1:
 1. Prior to dosing
 2. 4 hours (\pm 10 mins) post dose
- Day 14:
 1. Prior to dosing
 2. 4 hours (\pm 10 mins) post dose

¹² The DSST, DCFS, MHYS, FOG-Q, C-SSRS, verbal fluency, and MoCA to be done by a qualified clinical rater.

¹³ MCI subjects only

¹⁴ Cohort B only; DLB and PDD subjects

¹⁵ RBD+PD, DLB and PDD subjects only

¹⁶ Cohort A only; MCI and RBD+PD subjects

¹⁷ RBD+PD subjects only

¹⁸ The RBD1Q, ESS, HADS, and GDS are per subject self-report.

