1.3. Overall Risk/Benefit Assessment

While there will be no direct benefits for subjects participating in this study, the data generated will be valuable and beneficial for developing β -AR agonist therapies for neurodegenerative diseases.

The adverse events (AEs) that are expected with use of CST-103 and CST-107 for their approved indications is provided in the Investigator Brochure (IB). The medications will be administered as daily doses in this study.

Hypokalemia is a known effect of β_2 -AR-agonists, but its clinical significance is unclear since it appears to be a redistribution of potassium in the body rather than total body potassium depletion (Unwin 2011, Kardalas 2018).

In CuraSen studies, CLIN-002 and CLIN-003, in which a total of 19 healthy subjects and 8 patients with PD were administered daily doses of 80 µg of CST-103 for 5-7 days only one case of mild hypokalemia was observed. It is therefore expected that hypokalemia will not be a safety concern with either β₂-AR-agonist. However, in case hypokalemia is observed during this study, the subject should be managed based on their clinical needs and presentation as appropriate as per the Investigator's discretion.

In cohort 8 from CLIN-002 when CST-103 was co-administered daily for seven days with CST-107 there were no clinically significant changes in vital signs, physical exam, ECGs, or laboratory values. Taken together with the decades of clinical safety data for CST-103 these safety results from our previous studies suggest that CST-103 will be generally well tolerated without any safety issues when co-administered with a 1 mg dose of CST-107.

Suicide ideation is always a concern for CNS-active drugs. There have been no reports of suicide due to clenbuterol, but subjects in this study will be monitored for suicide ideation.

Magnetic resonance imaging (MRI) is a painless and safe, non-invasive diagnostic procedure that uses a powerful magnet and radio waves to produce detailed images of the head or the body's organs and structures without the use of X-rays or other radiation.

There are no known harmful effects from the strong magnetic field used in MRI scans. However, the magnet is so powerful that it can affect any unsecured metal objects, which can be pulled toward the magnet. The magnet may affect pacemakers, artificial limbs, and other medical devices or implants that contain metal. The MRI will not be conducted if subjects have medical devices or implants.

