1.4.2. Rationale for Dose Selection

1.4.2.1. Rationale for CST-103 Dose Selection

CuraSen has initiated 3 signal-seeking clinical studies – CST101/CST107-CLIN-001 (CLIN-001), CST103/CST107/CST109-CLIN-002 (CLIN-002), and CST101/CST103/CST109-CLIN-003 (CLIN-003) – to evaluate the effects of β -AR agonists on cerebral perfusion as measured by ASL MRI and cognition. Observations from those studies inform the trial design, endpoints, and doses of CST-103 planned for this study.

The 80 μ g CST-103 dose was selected based on data from 2 CuraSen clinical studies:

- Study CST103/CST107/CST109-CLIN-002 (CLIN-002) evaluated single oral doses of 20, 40, 80, and 160 μ g CST-103 and once-daily oral doses of 80 μ g CST-103 for 7 days in healthy male subjects aged 40 to 55 years. This study (Cohort 4) is currently evaluating single oral doses of 80 μ g CST-103 administered a week apart in patients with MCI or PD.
- Study CST101/CST103/CST109-CLIN-003 (CLIN-003) evaluated a single oral dose of 160 μ g CST-103 and once-daily oral doses of 80 μ g CST-103 administered for five days after 2 days of dose titration in healthy male and female subjects and in patients with PD.

[figure not shown]
The daily 80 µg CST-103 dose is below the recommended maximum daily dose in Germany (100 µg) for the treatment of reactive airways diseases. Preliminary data from a cohort of healthy subjects (n=16) and patients with Parkinson's disease (n=8) who were administered 80 µg CST-103 daily for 5 days after a two day dose titration in CLIN-003 demonstrate that CST-103 was in general well tolerated. There were no serious AEs, and all adverse events were rated as mild with the exception of two cases of musculoskeletal pain which were labeled as moderate. No clinically significant lab values were reported.

A cohort of healthy subjects (n=4) in CLIN-002 were administered once-daily oral doses of 80 µg CST-103 for 7 days without dose titration and this regimen was tolerated. There were no SAEs, no stopping criteria were met, and no rescue medications were used. All adverse events were rated as mild with the exception of a case of increased CK labeled as moderate. There were no clinically significant changes in vital signs, physical examinations, or ECGs. Hypokalemia (3.17 mg/dl) was observed in one subject but was transient.

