Data from Cohort 2 in CLIN-002, in which subjects received a single oral dose of 160 µg CST-103, demonstrated that CST-103 at this higher dose was generally well tolerated in the healthy subjects. Mild hypokalemia and hyperglycemia were observed with spontaneous recovery within the next few hours. One subject experienced mild sinus tachycardia and palpitations after dosing with CST-103. A favorable safety and tolerability profile of the planned CST-103 dose is also supported by published clinical studies, including a 52-week, double-blind, randomized, placebo-controlled study of CST-103 80 µg twice daily ([Koeberl 2018](#)).

The neuroimaging data from CLIN-002 using ASL MRI demonstrated that doses of CST-103 below 30 µg do not produce significant increases in cerebral perfusion and a dose of 40 µg produces a minimal increase while doses of 80 and 160 µg produce a robust global increase in cerebral perfusion, with a particularly robust increase of up to 15% in the thalamus and up to 28% in the hippocampus, which are both areas of the brain relevant to neurodegenerative diseases ([Figure 1](#), [Bartsch 2015](#), [Leh 2016](#)).

Figure 1: CST-103 Produces a Dose-Dependent Increase in Cerebral Perfusion (measured as cerebral blood flow [CBF]) in the Thalamus and Hippocampus as Measured by ASL-MRI

In Cohort 5 of CuraSen study CLIN-002, “estimated doses” of CST-103 were based on dose equivalents calculated from PK modeling of exposures at 24 hours (estimated dose of 50 µg) and 48 hours (estimated dose of 30 µg) after a single dose of 80 µg CST-103 administered to subjects on Day 1. On days when CST-103 was dosed ASL was conducted 3 hours post dosing.

Our hypothesis is that by improving cerebral perfusion, particularly in areas of the brain that are relevant for symptoms that are commonly found in PD and MCI, the administration of a β -AR agonist will have a positive effect on clinically relevant symptoms such as memory and cognition. In particular for cognition, preliminary data from study CLIN-003 suggest that a daily dose of 80 µg of CST-103 improves cognitive performance in healthy subjects.

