1.5. Rationale for CST-107 Dose Selection

CST-107 is included in this study to attenuate the peripheral effects commonly caused by β_2 -AR agonists which include increased heart rate, palpitations, tremors, decreases in potassium and increases in blood glucose. Previous CuraSen studies exploring low doses of CST-107 co-administered with 80 μg of CST-103 suggest that a 1 mg dose can attenuate these peripheral effects. This is in marked contrast to the usual initial dose for hypertension which is 40 mg CST-107 tablets once daily. The usual maintenance dose is 40 or 80 mg administered once daily and doses up to 240 or 320 mg administered once daily may be needed.

In the treatment of reactive airways disease, the use of a β -AR blocker is not normally recommended along with CST-103 in that the therapeutic effect of the agonist can be antagonized and would risk triggering a severe bronchospasm in patients with asthma. Since this study does not include patients with reactive airways disease and CST-103 is not being used for its bronchodilatory properties, this contraindication is not applicable to this study.

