- Vital signs (BP, HR, respiration rate, and oral/tympanic temperature); BP and HR measurements obtained 3 times (separated by approximately 1 minute) after the subject is supine for 5 minutes:
 - 1 hour (± 30 minutes) after dosing
- C-SSRS
- FERT, administered after dosing
- CANTAB and verbal fluency test (alphabet & category):
 - Up to 4 hours post dose

- PLR test (twice for each eye), after the post dose CANTAB
- GDS
- ESS

5.1.1.5. Day 14 (± 1), Treatment Periods 1 and 2 / Early Withdrawal (EW)

The following procedures will be performed, and assessments/measurements recorded:

- Assessment of concomitant medications
- Assessment of AEs
- Collection of subject dosing diary
- Administer study medication and collect bottles for accountability
- Vital signs (BP, HR, respiration rate, and oral/tympanic temperature); BP and HR measurements obtained 3 times (separated by approximately 1 minute) after the subject is supine for 5 minutes:
 - 1 hour (± 30 minutes) after dosing
- 12-lead ECG, obtained after subject has rested in supine position for at least 5 minutes:
 - 1 hour (± 30 minutes) after dosing
 - 4 hours (± 30 minutes) after dosing
- C-SSRS
- Laboratory tests – subjects should be fasting for 8 hours prior to the safety labs
 - Hematology, chemistry, and urinalysis
 - Serum or urine pregnancy test (per standard site practice) for females of childbearing potential; positive urine pregnancy result to be confirmed by serum test
- PK samples:
 - Prior to dosing
 - 4 hours (± 10 minutes) post dose
- Pharmacodynamic sample collection 4 hours (± 10 minutes) post dose
- BioStamp collected
- FERT, administered after dosing
- CANTAB and verbal fluency (alphabet & category)
 - Up to 4 hours post dose
- PLR test (twice for each eye), after the post dose CANTAB
- HADS
- GDS
- ESS
- FOG-Q (RBD+PD subjects only)
- Schedule Follow-Up Visit

5.1.1.6. Follow-Up – 14 (± 3) Days after Treatment Period 2 Day 14 or EW Visit

The following procedures will be performed, and assessments/measurements recorded:

- Vital signs (BP, HR, respiration rate, and oral/tympanic temperature); BP and HR measurements obtained 3 times (separated by approximately 1 minute) after the subject is supine for 5 minutes

- 12-lead ECG, obtained after subject has rested in supine position for at least 5 minutes
- Symptom-driven physical examination
- C-SSRS
- Laboratory tests – subjects should be fasting for 8 hours prior to the safety labs
 - Hematology, chemistry, and urinalysis

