7.2. Study Medication Dosing and Administration

Study treatments are:

- CST-103/CST-107 PO taken in the morning after the first meal of the day during each Treatment Period:
 - 80 µg CST-103, administered as two 40 µg capsules QD Day 1 – Day 14

- 1 mg CST-107, administered as one 1 mg capsule QD Day 1 – Day 14
- Matching placebo taken daily during each Treatment Period

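### Safety labs have no dose-relative draw time, and the 8 h fast with after-meal dosing means a short-lived potassium or glucose change after a dose would generally not be sampled

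*Protocol*

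**What the plan says.** **Lab timing.** The Schedule of Events puts safety labs at Screening, Day 1, Day 14 and Follow-Up, with none on Day 7. Footnote 8 gives the fasting condition and nothing else about timing: "Subjects should be fasting for 8 hours for the safety labs". The visit lists in Protocol 5.1 repeat it: "subjects should be fasting for 8 hours prior to the safety labs". Protocol 5.3.3 refers back to the Schedule of Events for timepoints, and cites the Laboratory Manual only for sample processing and shipping.

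**Dosing.** Under Protocol 7.2 the drug is "PO taken in the morning after the first meal of the day during each Treatment Period". The interval between meal and dose is not given.

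**Other measurements.** Vital signs (footnote 5), ECGs (6), PK samples (11) and pharmacodynamic samples (27) all carry times relative to dose. Blood is already drawn for PK at 4 h (±10 min) after dosing on Days 1 and 14 of each period.

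**Expected effects.** Protocol 1.5 says CST-107 is included to attenuate class effects that include "increased heart rate, palpitations, tremors, decreases in potassium and increases in blood glucose". On a single 160 µg dose, Protocol 1.4.2.1 reports: "Mild hypokalemia and hyperglycemia were observed with spontaneous recovery within the next few hours".

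**Analysis.** Laboratory tests are part of a secondary endpoint comparing the combination with placebo (Protocol 2.3). Protocol 8.8.8 summarizes labs by treatment. SAP 10 summarizes them by treatment sequence. SAP 10.2 reports labs by visit, whereas SAP 10.3 and 10.4 report vital signs and ECGs by visit and timepoint. SAP 10.2 names potassium and glucose for optional box plots.

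**The concern.** Potassium and glucose are the two analytes for which the protocol itself describes an acute drug effect, and the only time course it reports is recovery within hours. If compliant blood is taken before the dose or late in the day, a brief change will not appear in the scheduled chemistry. A clean lab table could then be read as evidence that CST-103 with CST-107 has no acute metabolic effect, when those hours were not sampled.

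The labs are also reviewed at the Safety Review Meetings (Protocol 3.2), can contribute to stopping a subject's dosing (3.3), and can generate adverse events (6.2).

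A second problem is labeling. The fast is worded as a should, so some sites may draw after dosing. SAP 6.5 analyzes nominal visits without windowing, so pre-dose and post-dose values could sit under one visit label.

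**Working it through.** The plan states no figure on this point, so there is nothing to reproduce. The check is on timing.

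**Inputs**
- Fast required before the draw: 8 h (footnote 8).
- Dose follows the first meal (Protocol 7.2).
- Meal-to-dose gap *g*: not in the documents, so it is assumed and varied.
- Existing post-dose draw: 4 h ± 10 min (footnote 11).

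**When can a compliant panel be drawn?** It comes either before the meal, hence before the dose, or at least 8 h after the meal. In the second case the earliest draw is 8 − *g* hours after the dose. The fast reached by the 4 h draw is 4 + *g* hours.

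| *g* (h) | Earliest compliant post-dose draw, 8 − *g* (h) | Fast at the 4 h draw, 4 + *g* (h) |
|---|---|---|
| 0 | 8 | 4 |
| 0.5 | 7.5 | 4.5 |
| 1 | 7 | 5 |
| 2 | 6 | 6 |
| 4 | 4 | 8 |

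For gaps of 0 to 2 h, the earliest compliant post-dose draw is 6 to 8 h after dosing. The 4 h draw meets the fast only if the meal ended about 4 h before the dose and nothing was eaten after it.

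**What each panel can show**
- Day 1, drawn before the meal: a baseline, with no first-dose response.
- Day 14, drawn before the meal: about 24 h after the Day 13 dose, during continued daily dosing. A sustained shift is visible; a change lasting a few hours is not.
- Early withdrawal: possibly more than a day after the last dose.

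**Prior experience at 80 µg daily.** Protocol 1.3 counts 19 healthy subjects and 8 with PD, so 19 + 8 = 27, and reports that "for 5-7 days only one case of mild hypokalemia was observed". That is 1/27 = 3.7%, exact 95% CI 0.1% to 19.0%. The cohorts described in Protocol 1.4.2.1 add to 16 + 8 + 4 = 28, which does not match. With 28 the rate is 1/28 = 3.6%, so the mismatch does not change the picture.

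**Size of the addition.** 2 analytes × 2 days × 2 periods = 8 results per subject; × 40 subjects = 320.

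**The case against.** The sponsor considered this risk openly. Protocol 1.3 describes the hypokalemia as apparent redistribution of potassium, regards its clinical significance as unclear and does not expect it to be a safety concern. Protocol 5.5 considers it unlikely with CST-107. Potassium below normal is addressed in exclusion criterion 5. ECGs at 1 h and 4 h, vital signs at 1 h and adverse event collection already cover the post-dose hours, and unscheduled labs are possible. When the combination was given for seven days, "there were no clinically significant changes in vital signs, physical exam, ECGs, or laboratory values". The within-hours evidence comes from twice the study dose without CST-107. The study is small and descriptive, and a 4 h sample may itself miss the extreme value.

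Most of this stands, and it is why severity is low. It does not close the gap. ECG, vital signs and symptoms do not measure potassium or glucose. The size of the combination cohort and its lab draw times are not given. The low potassium at 80 µg is described only as follows: "Hypokalemia (3.17 mg/dl) was observed in one subject but was transient". No time course is stated, so it does not show whether the change was brief within a day or lasted longer.

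The recording part of the fix is partly in place: SAP 7.7 lists dose times, and SAP 5 sorts listings by assessment time where available. Neither sets a draw time.

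A reader might infer that the trial cannot detect hypokalemia or hyperglycemia at all. The documents do not support that, because the Day 14 panel falls under continued dosing. Nor do they establish that every panel is pre-dose: that timing is inferred, the fast is not absolute and the meal-to-dose gap is unstated.

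**Conclusion.** The point holds as a gap in sampling acute change. A compliant Day 1 or Day 14 panel is most likely pre-dose, and otherwise roughly 6 to 8 h or more after the dose. A short-lived potassium or glucose change, including after the first dose, would generally not be captured by scheduled labs. This rests on compliance with the fast and on an assumed meal-to-dose gap of 0 to 2 h.

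Severity is low. The documents contain no evidence of an acute laboratory problem with 80 µg CST-103 plus 1 mg CST-107, and no figure for the size of any acute change at that regimen. The trial's validity is not threatened.

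A reader might also infer that better-timed labs would test whether CST-107 attenuates these effects. They would not: there is no CST-103-alone arm, so only the combination can be compared with placebo.

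The SAP's display by sequence departs from Protocol 8.8.8 and does not give the direct drug-versus-placebo comparison named in the secondary endpoint. It is a separate inconsistency and adds no weight to the timing gap, but correcting it costs nothing.

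**What to change.** **Protocol, footnote 8 and matching visit lists.** State that fasting safety labs on Days 1 and 14 are drawn before dosing, with the draw time and last-dose time recorded, including at early withdrawal. Add non-fasting potassium and glucose to the existing 4 h (±10 min) post-dose draw on Days 1 and 14 of both periods.

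**SAP 10 and 10.2.** Summarize all labs by treatment, not only by sequence. Summarize potassium and glucose also by timepoint (pre-dose, 4 h), descriptively, against the same timepoint in the placebo period; this serves as the control for the non-fasting sample. Note that 4 h may miss the potassium nadir or glucose peak, so a normal value does not exclude an earlier change.

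**Cost.** Eight extra results per subject (320 for 40 subjects) for the investigator to review, and possibly an extra tube; the Laboratory Manual is not available to check. No new visit or venepuncture is needed. Both regional protocols (SAP 2.1) need amendment with ethics committee approval, plus the SAP wording.

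**If the assays are not added, or dosing is complete.** Report Day 14 chemistry by recorded time since last dose, by treatment, and draw no conclusion about acute potassium or glucose effects.

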1. INTRODUCTION

1.1. Background: Neurodegenerative Disease

1.1.1. Parkinson's Disease

Parkinson's disease (PD) was originally described by James Parkinson in the 19th century and named the "shaking palsy" (Parkinson 1817). PD affects 0.1% to 0.2% of the general population with increasing prevalence with age and up to 1% in individuals above 60 years of age, resulting in an estimated 7 to 10 million people with PD worldwide (Tysnes and Storstein 2017).

PD is a common, progressive and debilitating neurodegenerative disease classically characterized by motor symptoms, including tremor, muscle rigidity, bradykinesia, and posture balance disorders (Kalia 2015). In addition to these classic motor symptoms, the physical burdens for PD patients include nonmotor symptoms, including cognitive dysfunction, neuropsychiatric symptoms, autonomic dysfunction, sleep disorder, and sensory dysfunction (Boland and Stacy 2012). An increasing amount of clinical and epidemiological data suggest that these nonmotor symptoms contribute throughout the entire course of PD.

PD is characterized by the progressive loss of dopaminergic neurons in the substantia nigra and by the appearance of Lewy bodies, which are intracellular inclusions of aggregated α -syn, a protein that is considered to play an important role in the pathogenesis of PD (Dehay 2015).

1.1.2. Mild Cognitive Impairment

Alzheimer's disease (AD) is a severe and life-threatening neurodegenerative disorder that affects approximately 44 million people in the world. Pathological hallmarks of AD include synaptic and neuronal loss, neuroinflammation, alterations of various neurotransmitter systems, and the accumulation of amyloid plaques and neurofibrillary tangles (Huang 2012). The approved medications that are currently available to treat AD provide transient palliative care for some patients but do not alter progression of the disease. Therefore, there is an urgent need for developing therapeutic agents capable of simultaneously addressing cognitive symptoms and pathology of AD and its precursor, amnesic mild cognitive impairment (MCI).

Evidence from both genetic at-risk cohorts and clinically normal older individuals suggests that the pathophysiological process of AD begins years, if not decades, before the diagnosis of clinical dementia during the preclinical stage of AD (Sperling 2011). Preclinical AD is the stage where subjects have amyloid deposition but do not yet have any symptoms (Buckley 2018). In contrast, patients who are at the MCI stage have cognitive deficits. Of interest is that one of the early changes seen in the preclinical stage of AD are areas of decreased cerebral perfusion that are indicative of the diagnosis (Musiek 2012) and measurement of these hypoperfusion areas have been shown to be useful as a biomarker for AD (Jack 2013).

Cerebral perfusion can be measured by arterial spin labeling perfusion magnetic resonance imaging (ASL MRI) (Fällmar 2017). ASL enables the measurement of brain perfusion non-invasively at the tissue level (Haller 2016) by utilizing magnetically labeled blood water as an endogenous tracer.

